2.4.2 Secondary endpoints/outcomes

- Proportion of patients with HIV-RNA viral load < 50 copies/mL at week 24, 36, 48
- HIV-1 drug resistance at confirmed virological failure (genotype)
- Time to reach CD4 count > 200/ μ L (first measurement)
- Proportion of patients with CD4 cell count < 200 μ L and < 350 μ L at week 4, 8, 12, 24, 36, 48
- CD4/CD8 ratio at week 4, 8, 12, 24, 36, 48
- Incidence of IRIS in the two arms through week 48
- Incidence and duration of hospitalisation, rate of relapse of specific OI/BI through week 48
- Safety and tolerability, measured by Grade 2, 3 and 4 signs and symptoms and laboratory toxicities through week 48
- ART and OI/BI treatment changes and dose modifications due to toxicities and DDI with ART, and IRIS through week 48
- Health care resource use, including total inpatient days and emergency room visits through week 48
- QOL and functional status outcomes, including overall self-reported QOL and functional status compared in the two groups at week 48
- Discontinuation or modification of study medication due to insufficient virological response, resistance mutations at baseline, or resistance mutation development before week 48

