The incidence of hospitalisation will be estimated by the Kaplan-Meier estimate. The Log-rank test will be used to compare the two survival functions. The duration of hospitalisation will be estimated by the cumulative days of hospitalisation during the course of study and will be compared between the 2 groups by using the Mann-Whitney test. The rate of relapse/recurrence will be estimated by the number of patients with relapse/recurrence divided by the total number patients in ITT population. Fisher's exact test will be used to compare the 2 groups.

The frequency of each Grade 2, 3 or 4 AEs, laboratory toxicities, and ART and OI/BI treatment changes and dose modifications due to toxicities and IRIS will be described and compared by group. Fisher's exact test will be used to compare the 2 groups.

The proportion of patients with health care resource use, and emergency room visits will be compared in the two groups with Fisher's exact test. The total inpatient days will be estimated by the cumulative inpatient days during the course of study and will be compared between the 2 groups by using the Mann-Whitney test.

To assess the impact of study treatment on the evolution of QOL at week 48, we will use multiple imputation approach to replace missing values. We will compare the treatment effect on QOL on each of the 5 datasets generated, including the imputed values, and the results will be combined with Rubin's rules. A generalized estimating equation (GEE) model will be used.

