10. OTHER ANALYSES

10.1 OTHER SECONDARY ENDPOINTS

10.1.1 ART and/or opportunistic infection/bacterial infection treatment changes and/or dose modifications due to toxicities and/or DDI with ART, and/or IRIS through week 48

Endpoint

The endpoint is the proportion of patients with ART treatment changes and/or dose modifications due to toxicities and/or DDI with ART, and/or IRIS through week 48.

Descriptive statistics and graphical representation

The analyses will be performed with the mITT population and DPS1. Data will be summarised with the number and percentage of participants with ART or OI/BI treatment changes or dose modifications due to toxicities and DDI and IRIS through week 48. The list of patients with the event of interest will be reported in a table, including the previous and the current treatment, start date, end date and the reason for change.

Statistical methodology

The percentage of patients with ART n treatment changes due to toxicities and/or DDI with ART, and/or IRIS will be estimated by the number of patients with the event of interest divided by the total number patients in ITT population. The effect of study treatment on the proportion of patients with ART treatment changes due to toxicities and/or DDI with ART, and/or IRIS at week 48 will be assessed using a logistic regression model with treatment group and adjustments for stratification factor (country/group of neighbouring countries and baseline CD4 cell counts (<50 or \geq 50/ μ L)). An adjusted odds ratio (OR) and the associated 95% Confidence Interval (CI) will be calculated. Similar analyses will also be performed separately for each component (toxicities, DDI, and IRIS). If no events were observed in a group, the comparison will be made using Fisher's exact test.

10.1.2 Health care resource use, through week 48

Endpoint

The endpoint is the proportion of patients with health care resource use, through week 48.

Descriptive statistics and graphical representation

The analyses will be performed with the mITT population and DPS1. Data will be summarised with the number and percentage of participants with health care resource use, including total inpatient days and emergency room visits through week 48.

Statistical methodology

The percentage of patients with health care resource use, including total inpatient days and emergency room visits will be estimated by the number of patients with the event of interest divided by the total number patients in ITT population.

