The effect of study treatment on the proportion of patients with health care resource use, including total inpatient days and emergency room visits at week 48 will be assessed using a logistic regression model with treatment group and adjustments for stratification factor (country/group of neighbouring countries and baseline CD4 cell counts (<50 or $\geq 50/\mu\text{L}$)). An adjusted odds ratio (OR) and the associated 95% Confidence Interval (CI) will be calculated.

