Mean (95% CI) difference from baseline to week 48			

TABLE 7: SAFETY

	Integrase inhibitor (N=XXX) Person-Year (P-Y): XXX.X			Protease inhibitor (N=XXX) Person-Year (P-Y): XXX.X			P-value
	N of events	N of pts (%)	Incidence rate/100 p-y	N of events	N of pts (%)	Incidence rate/100 p-y	
Any adverse events (AEs : grade ≥2)							
Grade 2							
Grade 3							
Grade 4							
Grade unknown							
Grade 3 or 4 AE							
Drug related AEs							
Drug related grade 3/4 AEs							
dress syndrom (rash)							
IRIS							
IRIS-Kaposis sarcoma							
PML-IRIS requiring hospitalisation							
progressive rash							
transaminitis							
worsening symptoms of Progressive multifocal leukoencephalopathy							
....							
....							
AE leading to the study drugs interruption							
Serious adverse events (SAE)							
Laboratory toxicities							
Death							

TABLE 8. OTHER SECONDARY ENDPOINTS

	Integrase Inhibitor	Protease Inhibitor	Adjusted OR	P-value
	N=XXX	N=XXX	(95% CI)	
Percentage of patients with HIV drug resistance mutations among those with virological failure				
Proportion of patients with ART treatment changes due to toxicities and/or DDI with ART, and/or IRIS through week 48 - due to toxicities - due to DDI - due to IRIS				
Proportion of patients with with health care resource use, including total inpatient days and emergency room visits through week 48				
Proportion of patients with discontinuation or modification of study medication due to insufficient virological response or resistance mutations development before week 48 - for insufficient virological response - resistance mutations development				
Proportion of patients for whom there is a difference in the list of mutations (Stanford list last available version) detected by deep sequencing compared with those detected by population sequencing				

TABLE 9: EVOLUTION OF QUALITY OF LIFE (HEALTH STATUS SCORE) AND HIV SYMPTOMS INDEX

Week	QOL : health status score			HIV Symptoms index score		
	Integrase Inhibitor	Protease Inhibitor	P-value between groups	Integrase Inhibitor	Protease Inhibitor	P-value between groups
	Mean (SD)	Mean (SD)		Mean (SD)	Mean (SD)	
0						
4						
8						
12						
24						
36						
48						
Mean (SD) from baseline to W4						
Mean (SD) from baseline to W8						
Mean (SD) from baseline to W12						
Mean (SD) from baseline to W24						
Mean (SD) from baseline to W36						
Mean (SD) from baseline to W48						

TABLE 10: QUALITY OF LIFE DIMENSIONS: MOBILITY AND SELF- CARE

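### SAP 10.1.2 and Table 8 plan one yes/no comparison of health care resource use, so emergency room visits and cumulative inpatient days lose the separate comparisons planned in protocol 9.3.3

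*Combined protocol and SAP*

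**What the plan says.** Protocol v5.0 section 2.4.2 lists the secondary endpoint as "Health care resource use, including total inpatient days and emergency room visits through week 48", and SAP 2.2.2 lists the same endpoint with the same two parts.

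Protocol 9.3.3 says how they are to be analysed. On proportions: "The proportion of patients with health care resource use, and emergency room visits will be compared in the two groups with Fisher's exact test". On inpatient days: "The total inpatient days will be estimated by the cumulative inpatient days during the course of study", compared between the groups by a Mann-Whitney test. Protocol v1.5 carries the same text, and none of the listed amendments touches it.

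SAP 10.1.2 defines a single outcome: "The endpoint is the proportion of patients with health care resource use, through week 48". The treatment effect on the proportion with "health care resource use, including total inpatient days and emergency room visits at week 48 will be assessed using a logistic regression model", adjusted for the stratification factors. Table 8 has one row, "Proportion of patients with with health care resource use, including total inpatient days and emergency room visits through week 48", with no sub-rows.

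**The concern.** The protocol treats this endpoint as more than one quantity. The SAP collapses them into one proportion and gives no reason.

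Two planned comparisons are affected. Emergency room visits have no between-arm comparison of their own anywhere in the SAP. Cumulative inpatient days, which are a count, appear only inside a yes/no proportion, where a number of days has no meaning. Hospital admission is less exposed, because SAP 7.2.8 analyses first hospitalisation separately.

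If a participant with any admission already counts as a user of resources, an emergency visit by that participant adds nothing to the merged outcome. A difference between the regimens in emergency visits can then be diluted, and the comparison that would show it is not planned.

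**Working it through.** **Comparison of the texts.** This settles the point.

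| Quantity | Protocol 9.3.3 | SAP |
|---|---|---|
| Overall resource use | Proportion, Fisher's exact test | 10.1.2: one adjusted logistic model, one Table 8 row |
| Emergency room visits | Named among the proportions, Fisher's exact test | No comparison of their own |
| Cumulative inpatient days | Mann-Whitney test | No such comparison |

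Two checks on this reading:

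- The SAP separates components where it means to. Sections 10.1.1 and 10.1.4 each promise an analysis of every component, and their Table 8 rows list the components. Section 10.1.2 and its row do neither.
- SAP 7.2.9 does not replace the inpatient-days comparison. It is restricted to hospitalised participants and runs from the first admission to the last discharge. It leaves out those never admitted and counts any days spent at home between admissions.

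**Illustration of dilution.** The documents give no rate for emergency visits or admissions, so those rates are assumptions. Only the sample size and the two-sided 5% level come from the plan.

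The plan's sample size reproduces. Events = 4 × (1.960 + 0.842)² / (ln 1.606 − ln 0.909)² = 96.9, so 97. With an average failure probability of (25% + 23%)/2 = 24%, 97/0.24 = 404 participants, or 202 per arm. Allowing 7.5% dropout, 202/0.925 = 218.4, so 219 per arm against the planned 220.

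Let e be the proportion with an emergency visit, h the proportion admitted (equal in both arms), and s the share of emergency-visit patients who are also admitted. Taking use to mean an emergency visit or an admission, the merged proportion is h + e(1 − s). Independence means s = h. Power is the normal approximation for two proportions with n = 220 per arm:

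power = Φ{ [ |p₁ − p₂| − 1.96 √(2p̄(1 − p̄)/n) ] / √( [p₁(1 − p₁) + p₂(1 − p₂)]/n ) }

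Emergency visits alone, 10% v 20%: p̄ = 0.15, the two standard errors are 0.0340 and 0.0337, and power = Φ[(0.10 − 0.0667)/0.0337] = Φ(0.99) = 84%. The exact power of Fisher's test is 81%. The odds ratio is 2.25.

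The same difference inside the merged outcome:

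| Admissions, both arms | Independent: proportions | Power | 70% of emergency-visit patients admitted: proportions | Power |
|---|---|---|---|---|
| 20% | 28% v 36% | 44% | 23% v 26% | 11% |
| 30% | 37% v 44% | 32% | 33% v 36% | 10% |
| 40% | 46% v 52% | 24% | 43% v 46% | 9% |

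The merged odds ratio falls to between 1.45 and 1.27 under independence, and to between 1.18 and 1.13 with 70% overlap.

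A smaller effect, 7% v 15%, gives 77% power alone (73% by Fisher's test), 32% to 17% merged under independence, and 9% to 7% with 70% overlap.

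If admissions differ in the opposite direction (25% in the arm with 20% emergency visits, 32.5% in the arm with 10%), the merged proportions are 0.25 + 0.20 × 0.75 = 40.0% and 0.325 + 0.10 × 0.675 = 39.3%. The emergency-visit difference has gone.

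**The case against.** A reader might infer that a difference in emergency visits is necessarily masked, or could not be seen or reported at all. The documents do not support that. The descriptive paragraph of SAP 10.1.2 mentions inpatient days and emergency visits when it lists what will be summarised. Since a total of days cannot be a yes/no item, that phrase may be meant as a list of separate summaries. A descriptive report by arm is therefore not ruled out. What is missing is a planned comparison and a table row.

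A reader might also infer that the merged outcome largely repeats the hospitalisation analysis in SAP 7.2.8. That too goes beyond the text. Neither document defines resource use as an emergency visit or an admission, 7.2.8 is a time-to-first-event analysis, and no admission rate or overlap is given. The illustration takes that definition as an assumption.

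The protocol sentence on proportions is loosely punctuated and could be parsed as one combined proportion. Its separate naming of emergency visits makes two comparisons the more natural reading, and the loss of the inpatient-days comparison does not depend on it.

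Finally, this is one of 13 secondary endpoints in SAP 2.2.2, and SAP 5.1 allows the plan to be updated after a mock-up report and before sign-off. That limits the weight of the point and makes it easy to repair. It does not remove it.

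**Conclusion.** The point holds as a mismatch between the protocol and the SAP. As written, the SAP provides one yes/no comparison where protocol 9.3.3 also names emergency room visits and tests cumulative inpatient days separately. Emergency visits are left with no comparison of their own, and inpatient days with only the partial cover of 7.2.9.

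The loss of power is an illustration, not an estimate for this trial. For an assumed 10% v 20%, power falls from about 84% to between 44% and 24% if visits and admissions are independent with 20-40% admitted, and to about 10% if 70% of emergency-visit patients are also admitted. Those figures rest on assumed rates, an assumed definition of use, and 220 per arm with complete data. The mismatch itself rests on none of them.

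The endpoint is secondary, so the non-inferiority conclusion is unaffected. It should be corrected before the SAP is signed.

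**What to change.** In SAP 10.1.2 and Table 8:

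1. Add the proportion of participants with at least one emergency room visit through week 48 as an endpoint in its own right, analysed with the adjusted logistic model already stated there, with its own row.
2. Restore the between-arm Mann-Whitney comparison of cumulative inpatient days in the whole mITT population, with participants never admitted counted as zero days, and give it its own row.
3. Keep the overall resource-use comparison, since protocol 9.3.3 names it too, and state what counts as use.

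The cost is one model, one test and two table rows. No new data are needed provided the eCRF records emergency visits, as the listed secondary endpoint requires. That should be confirmed first, because the schedules of assessments in protocol Appendix 1 and SAP 3.3 show no item for them and a visit without admission need not be reported as a serious adverse event.

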10.1.3 Quality of life (EQ-5D-3L questionnaire) and HIV Symptoms index

Endpoints

The endpoints are:

- Change from baseline in health status score ranging from 0 to 100 (100 being best quality of life) and in each of the 5 dimensions of the EQ-5D-3L quality of life questionnaires (mobility, self-care, usual activities, pain/discomfort and anxiety/depression). Each dimension has 3 levels: 1=no problems, 2=some problems, and 3=extreme problems.
- Change from baseline in HIV symptoms index score over time. HIV Symptoms Index questionnaire is consisted of 20 selected symptoms. Each symptom has 5 levels: 0=I do not have this symptom 1=It doesn't bother me 2=It bothers me a little 3=It bothers me 4=It bothers me a lot. The HIV Symptom Index score is the sum of frequency ratings for the 20 selected symptoms; the score could range from 0 to 80.

Descriptive statistics and graphical representation

The analyses will be performed with the mITT population who complete the baseline questionnaire and least one of the follow-up questionnaires.

Data for health status score and HIV Symptoms index will be summarised by mean and standard error. The evolution of health status score and HIV Symptoms index will be described by boxplots for each treatment group at each time point.

Data for the 5 dimensions will be summarised with number and percentages per class and Bar plotted will also be generated for each of the 5 dimensions.

The number of participants with data available at each time point will also be reported.

Statistical methodology

The changes from baseline in health status score will be compared between the two treatment groups using mixed models for repeated measures with random intercept and slope and spatial power covariance structure due to unequal time intervals between visits, adjusted for country/group of neighbouring countries and baseline CD4 cell counts (<50 or $\geq 50/\mu\text{L}$). The model will include treatment group, time, interaction between treatment group and time, country/group of neighbouring countries and baseline CD4 cell counts (<50 or $\geq 50/\mu\text{L}$). Time will be modelled as categorical variables.

The distribution of each of the 5 dimensions (mobility, self- care, usual activities, pain/discomfort and anxiety/depression), will be compared between the two treatment groups at each timepoint using Chi-square test

The changes from baseline in Symptom index score will be compared between the two treatment groups using mixed models for repeated measures with random intercept and slope and spatial power covariance structure due to unequal time intervals between visits, adjusted for country/group of neighbouring countries and baseline CD4 cell counts (<50 or \geq 50/ μ L). The model will include treatment group, time, interaction between treatment group and time, country/group of neighbouring countries and baseline CD4 cell counts (<50 or \geq 50/ μ L). Time will be modelled as categorical variables. All p-values will be two-tailed, with a significant level of 0.05.

10.1.4 discontinuation or modification of study medication due to insufficient virological response or resistance mutation development before week 48

Endpoints

The endpoint is the proportion of patients with discontinuation or modification of study medication due to insufficient virological response or resistance mutation development before week 48.

Descriptive statistics and graphical representation

The analyses will be performed with the mITT population and DPS1. Data will be summarised with the number and percentage of participants with discontinuation or modification of study medication due to insufficient virological response or resistance mutation development through week 48. The list of patients with the event of interest will be reported in a table, including the reasons for discontinuation or modification of study medication.

Statistical methodology

The percentage of patients with discontinuation or modification of study medication due to insufficient virological response or resistance mutation development will be estimated by the number of patients with the event of interest divided by the total number patients in ITT population.

The effect of study treatment on the proportion of patients with discontinuation or modification of study medication due to insufficient virological response or resistance mutation development through week 48 will be assessed using a logistic regression model with treatment group and adjustments for stratification factor (country/group of neighbouring countries and baseline CD4 cell counts (<50 or \geq 50/ μ L)). An adjusted odds ratio (OR) and the associated 95% Confidence Interval (CI) will be calculated.

The analyses will also be performed separately for each component of the endpoint (insufficient virological response and resistance mutation development). If no events were observed in a group, the comparison will be made using Fisher's exact test.

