The evolution of the proportion of participants with CD4<200/ μ L and <350/ μ L over time will be compared between the 2 treatment groups (DRV/c versus BIC) using a Generalized Estimating Equation (GEE) models with independent covariance structure, binomial distribution and log link, to estimate the relative risk. The models will include treatment group, time, and interaction between treatment group and time. Time will be modelled as categorical variable. A relative risk (RR) and the associated 95% CI will be calculated. All P-values will be two-tailed with a significant level at 5%.

7.2.6 Change in CD4/CD8 ratio from baseline to week 48

Endpoints

The change in CD4/CD8 ratio from baseline to week 48.

Descriptive statistics and graphical representation

The analyses will be performed with the mITT population and DPS1. Data will be summarized in tables by mean and standard error. The evolution of CD4/CD8 ratio will be described by boxplots for each treatment group at each time point. The number of participants with data available at each time point will also be reported.

Statistical methodology

The mean change in CD4/CD8 ratio from baseline to week 48 will be compared between the 2 treatment groups using a mixed model with random intercept and slope and spatial power covariance structure due to unequal time intervals between visits. The models included treatment group, time, and interaction between treatment group and time. Time was modelled as a categorical variable. All P-values will be two-tailed with a significant level at 5%.

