10.1.6 Change from baseline in plasma and urine laboratory parameters

Endpoints

The endpoints are the change from baseline plasma and urine laboratory parameters

Descriptive statistics and graphical representation

The analyses will be performed with the mITT population and DSP1.

Data will be summarised by mean and standard error. The evolution will be described by boxplots for each treatment group at each time point.

Statistical methodology

The changes from baseline in haematology, chemistry, lipid and glycaemia will be compared between the two treatment groups using mixed models for repeated measures with random intercept and slope and spatial power covariance structure due to unequal time intervals between visits, adjusted for country/group of neighbouring countries and baseline CD4 cell counts (<50 or $\geq 50/\mu\text{L}$). The model will include treatment group, time, interaction between treatment group and time, country/group of neighbouring countries and baseline CD4 cell counts (<50 or $\geq 50/\mu\text{L}$). Time will be modelled as categorical variables.

All p-values will be two-tailed, with a significant level of 0.05.

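### The change-from-baseline mixed models omit the outcome's own baseline value, so precision is generally lost for quality of life, symptoms, CD4/CD8 ratio and laboratory values

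*Combined protocol and SAP*

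**What the plan says.** Four groups of continuous outcomes are analysed as change from baseline with random-intercept-and-slope mixed models.

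- **Health status score (SAP 10.1.3).** "The changes from baseline in health status score will be compared between the two treatment groups using mixed models for repeated measures". The fixed effects are then listed: "The model will include treatment group, time, interaction between treatment group and time, country/group of neighbouring countries and baseline CD4 cell counts", with CD4 split at 50/µL.
- **HIV Symptom Index (SAP 10.1.3).** "The changes from baseline in Symptom index score will be compared between the two treatment groups using mixed models for repeated measures", with the same list of terms.
- **Laboratory values (SAP 10.1.6).** "The changes from baseline in haematology, chemistry, lipid and glycaemia will be compared between the two treatment groups using mixed models for repeated measures", again with the same list. The note under mock Table 16 extends the model to continuous urine parameters.
- **CD4/CD8 ratio (SAP 7.2.6).** "The mean change in CD4/CD8 ratio from baseline to week 48 will be compared between the 2 treatment groups using a mixed model". Here the list is shorter: "The models included treatment group, time, and interaction between treatment group and time".

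Tests are two-sided at 5%. None of the lists contains the baseline value of the outcome being modelled, and nothing elsewhere supplies it. SAP 5.3 adds only imputation and missing-visit rules. Protocol 9.3.3 planned a Mann-Whitney test on change in CD4/CD8 and a GEE for quality of life, and named no baseline covariate for either.

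The schedule in SAP 3.3 already collects the baseline values. SAP 10.1.3 also limits its analysis to participants with a completed baseline questionnaire.

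**The concern.** Subtracting the baseline is not the same as adjusting for it. The change score fixes the slope of follow-up on baseline at 1, whereas the true slope is usually lower. The excess subtraction adds noise. It also means that an arm which happens to start higher will tend to show a smaller gain, through regression to the mean. Adjusting for the measured baseline removes both effects.

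Baseline CD4 in two classes does not do this job. It is a stratification factor, and it recovers only what it predicts of each outcome's baseline. The CD4/CD8 model lacks even that.

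At stake are the width of the intervals for these secondary and other endpoints, and how far each estimate depends on chance differences at entry.

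**Working it through.** **Inputs.** The planned size is 220 per arm (SAP 4). That figure was set for the primary time-to-event endpoint; the documents state no power or precision for the change-from-baseline models. It reproduces:

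- Margin: ln(0.63)/ln(0.75) = 1.606. Expected hazard ratio: ln(0.77)/ln(0.75) = 0.909.
- These give 97 events at 80% power and two-sided 5%. Then 97/0.24 = 404 evaluable, or 202 per arm.
- 202/(1 − 0.075) rounds up to 219, against the stated 220.

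Here 220 serves only as n. The correlation rho between baseline and week 48, and the two SDs, are **assumed**.

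**Equal SDs.** In SD² units, the variance of the arm difference is

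- change score: 2(1 − rho) × 2/n
- adjusted for baseline: (1 − rho²) × 2/n

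so the ratio of interval widths is √(2/(1 + rho)). The half-width is 1.96 × the square root of the variance. For example, at rho 0.3 the planned half-width is 1.96 × √(1.4 × 2/220) = 0.221.

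| rho | Half-width, planned (SD) | Half-width, adjusted (SD) | Width ratio |
|---|---|---|---|
| 0.3 | 0.221 | 0.178 | 1.24 |
| 0.5 | 0.187 | 0.162 | 1.15 |
| 0.7 | 0.145 | 0.133 | 1.08 |

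Over rho 0.2 to 0.8 the ratio runs from 1.29 to 1.05.

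**Unequal SDs.** With k = baseline SD / week-48 SD, the width ratio is √((1 + k² − 2·rho·k)/(1 − rho²)). At rho 0.5:

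| k | Width ratio |
|---|---|
| 0.4 | 1.01 |
| 0.5 | 1.00 |
| 0.7 | 1.03 |
| 1.0 | 1.15 |
| 1.3 | 1.36 |

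The loss vanishes where the slope on baseline, rho/k, is close to 1.

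**Chance imbalance.** A baseline difference D shifts the change-score estimate by −(1 − rho/k)·D. At 220 per arm, the 95% range for D reaches 1.96 × √(2/220) = 0.187 SD. With k = 1, the shift at that edge is 0.131, 0.093 or 0.056 SD for rho 0.3, 0.5 or 0.7, in the direction opposite to D.

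**If week 0 is a response row.** Mock Tables 6, 9 and 15 list week 0 among the visits, so the model could be one of raw values with change taken as a contrast. The treatment main effect then leaves each arm's baseline mean free. I checked this by generalised least squares at weeks 0, 4, 8, 12, 24, 36 and 48. The assumed covariance had intercept variance 0.4, slope variance 0.15 per 48 weeks, and a spatial-power component of variance 0.6 with correlation 0.93 per week. It implies rho 0.39 and SDs of 1.00 at baseline and 1.07 at week 48.

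| Dropout | SE, baseline means free | SE, common baseline mean | Ratio |
|---|---|---|---|
| 0% | 0.1093 | 0.0941 | 1.16 |
| 7.5% | 0.1121 | 0.0974 | 1.15 |
| 20% | 0.1178 | 0.1039 | 1.13 |

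With complete data the first SE equals the change-score SE, and the second equals the baseline-adjusted SE.

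**The case against.** The strongest reply has five parts.

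1. **The SAP does not settle the response.** If week 0 is a response row, adding baseline as a covariate would put the same measurement on both sides of the model. This stands, and it decides which remedy is valid. It does not remove the loss, as the last table shows.
2. **Randomisation protects the comparison.** This also stands. A reader might infer that the planned estimates are biased. They are not, on average, and type I error is unaffected. What remains is lost precision, and a shift conditional on the imbalance actually realised.
3. **The size is assumed.** Correct. Equal SDs are doubtful for CD4/CD8: entry is mainly through low CD4 or AIDS, and SAP 6.5 expects few participants at 200/µL or above. Baseline ratios may be compressed and later ones more spread, so the loss there could be close to nil. The formulas also ignore the country and CD4 terms already in 10.1.3 and 10.1.6, which may recover part of it.
4. **Baseline values are not guaranteed for everyone.** Indirect bilirubin, urinary phosphate and beta-2 microglobulin, for example, are not mandatory. But a change score cannot be formed without a baseline value, so on that reading the covariate excludes nobody further.
5. **The consequence is limited.** These are secondary or other endpoints with no stated power, and the protocol promised no baseline adjustment.

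**Conclusion.** The concern holds as a worthwhile, low-cost improvement to secondary analyses. All four groups of models omit the outcome's own baseline value. In large samples the planned intervals are never narrower than baseline-adjusted ones and are generally wider: by about 24%, 15% or 8% at rho 0.3, 0.5 or 0.7 with equal SDs. Both rho and the SD ratio are assumptions. The loss may be near zero for CD4/CD8, and it is larger for any outcome whose baseline SD exceeds its follow-up SD.

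Two further inferences are tempting and should not be drawn. The equal-SD variance ratio (1 + rho)/2 could be read as a need for 18% to 54% more patients (1/0.85 − 1 to 1/0.65 − 1, for rho 0.7 to 0.3); the sample size was never set on these outcomes. Nor does the point reach every continuous secondary endpoint: duration of hospitalisation, for one, is analysed by Kaplan-Meier and Cox methods (SAP 7.2.9). The primary Cox analysis and its sample size are untouched.

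**What to change.** In SAP 7.2.6, 10.1.3 and 10.1.6, first state which visits form the response. Then:

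- **Post-baseline visits only:** add the outcome's baseline value and its interaction with time as covariates.
- **Week 0 as a response row:** constrain the baseline mean to be equal across arms, and do not add baseline as a covariate.

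The cost is small but not nil. The first option adds up to six parameters per model (weeks 4, 8, 12, 24, 36 and 48), repeated over many laboratory outcomes, which is minor at about 400 patients. The second uses 13 treatment-and-time mean parameters (seven visit means and six treatment contrasts) in place of 14. No new data are needed. SAP 5.1 allows updates before the final version is signed off, and the choice should be made then, because baseline adjustment added after results are seen would look data-driven.
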